## 4.2 EXCLUSION CRITERIA

1. Aggressive histological variants: blastic and pleomorphic variants (blastoid).
2. Proliferation index measured by Ki-67 > 30%.
3. B-cell monoclonal lymphocytosis with MCL phenotype.
4. Eastern Cooperative Oncology Group (ECOG) performance status  $\geq 2$ .
5. Presence of B symptoms or any relevant symptoms related to the MCL.
6. Nodal clinical forms with lymph node enlargement > 3 cm (maximum diameter).
7. Cytopenias attributable to MCL: Neutrophil count <  $1 \times 10^9/L$ , Hemoglobin level < 100 g/L or platelet count <  $100 \times 10^9/L$ .
8. Organ dysfunction related to MCL including creatinine level > 2 ULN or altered liver biochemistry (> 3x ULN).
9. Gradual increase in different determinations of serum LDH attributable to MCL that exceeds 20% of the ULN.
10. Known CNS infiltration.
11. Subjects with expected therapy requirement for MCL in a short time (< 3 months).
12. Patients with active hepatitis B or C infection or HIV infection. Positive test results for chronic HBV infection (defined as positive HBsAg serology) or positive test results for hepatitis C (hepatitis C virus [HCV] antibody serology testing) will be excluded with the following exceptions. Patients with occult or prior HBV infection (defined as negative HBsAg and positive total HBcAb) may be included if HBV DNA is undetectable, provided that they are willing to undergo monthly DNA testing or antiviral prophylaxis. Patients who have protective titers of hepatitis B surface antibody (HBsAb) after vaccination or prior but cured hepatitis B are eligible. Patients positive for HCV antibody are eligible only if PCR is negative for HCV RNA.
13. Anticoagulation requirement with vitamin K antagonists.
14. Past medical history of stroke or intracranial haemorrhage within 6 months prior to inclusion.
15. Required medication with strong CYP3A4/5 inhibitors.
16. Any serious comorbidity that makes the patient unacceptable for receiving the treatment
17. Concomitant or previous malignancies the last 2 years other than basal skin cancer or in situ uterine cervix cancer.
18. Pregnancy or lactation.
19. Major surgery within 4 weeks of inclusion.
20. Clinically significant cardiovascular disease such as uncontrolled or symptomatic arrhythmias, congestive heart failure, or myocardial infarction within 6 months of Screening, or any Class 3 (moderate) or Class 4 (severe) cardiac disease as defined by the New York Heart Association Functional Classification.
21. Vaccinated with live, attenuated vaccines within 4 weeks of randomization.
22. Uncontrolled systemic infection requiring intravenous (IV) antibiotics.
23. Any life-threatening illness, medical condition, or organ system dysfunction which, in the investigator's opinion, could compromise the subject's safety, interfere with the absorption or metabolism of ibrutinib capsules, or put the study outcomes at undue risk.

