	
active must be practising a highly effective method of birth control during and after the study consistent with local regulations regarding the use of birth control methods for subjects participating in clinical trials. Men must agree to not donate sperm during and after the study. For females, these restrictions apply for 1 month after the last dose of study drug. For males, these restrictions apply for 3 months after the last dose of study drug.
 
12. Women of childbearing potential must have a negative serum (beta-human chorionic gonadotropin [-hCG]) or urine pregnancy test at Screening. Women who are pregnant or breastfeeding are ineligible for this study.
 
13. Sign (or their legally-acceptable representatives must sign) an informed consent document indicating that they understand the purpose of and procedures required for the study, including biomarkers, and are willing to participate in the study.
 
EXCLUSION CRITERIA
 

1. Aggressive histological variants: blastic and pleomorphic variants (blastoid).

2. Proliferation index measured by Ki-67 > 30%.

3. B-cell monoclonal lymphocytosis with MCL phenotype

4. Eastern Cooperative Oncology Group (ECOG) performance status <math>\geq 2</math>.

5. Presence of B symptoms or any relevant symptoms related to the MCL.

6. Nodal clinical forms with lymph node enlargement > 3 cm (maximum diameter).

7. Cytopenias attributable to MCL: Neutrophil count < <math>1 \times 10^9/L</math>, Hemoglobin level < 100 g/L or platelet count < <math>100 \times 10^9/L</math>.

8. Organ dysfunction related to MCL including creatinine level > 2 x ULN or altered liver biochemistry (> 3x ULN).

9. Gradual increase in different determinations of serum LDH attributable to MCL that exceeds 20% of the ULN.

10. Known CNS infiltration.

11. Subjects with expected therapy requirement for MCL in a short time (< 3 months)

12. Patients with active hepatitis B or C infection or HIV infection. Positive test results for chronic HBV infection (defined as positive HBsAg serology) or positive test results for hepatitis C (hepatitis C virus [HCV] antibody serology testing) will be excluded with the following exceptions. Patients with occult or prior HBV infection (defined as negative HBsAg and positive total HBcAb) may be included if HBV DNA is undetectable, provided that they are willing to undergo monthly DNA testing or antiviral prophylaxis. Patients who have protective titers of hepatitis B surface antibody (HBsAb) after vaccination or prior but cured hepatitis B are eligible. Patients positive for HCV antibody are eligible only if PCR is negative for HCV RNA.

13. Anticoagulation requirement with vitamin K antagonists.

14. Past medical history of stroke or intracranial haemorrhage within 6 months prior to inclusion.

15. Required medication with strong CYP3A4/5 inhibitors

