Among the new drugs under development, Ibrutinib is showing an impressive efficacy in relapsed and refractory patients (8-9), which has led to its approval by the FDA and EMA agencies, in this context. Ibrutinib alone is able to induce 68% of responses in heavily pre-treated patients with MCL, including up to 21% of complete responses. The median time to achieve a CR was of 5.5 months (2-12 months). Moreover, ibrutinib in combination with rituximab appears to be a feasible and highly effective treatment in the relapse and refractory setting. The overall response rate was superior to 85%, including CR in 38% of cases. Moreover, MCL patients with a lower proliferation index (Ki-67 < 50%) achieved CR in up to 48% of the cases.

These promising results provide an excellent opportunity of treating in front-line selected MCL patients with a chemo-free approach, probably this resulting in a more efficient and less toxic manner of treating these patients. In this sense, we hypothesize that MCL cases with an indolent clinical presentation, not requiring the immediate initiation of therapy, would be excellent candidates to receive Ibrutinib in combination with rituximab in first line treatment.

Likewise, this trial offers an unbeatable platform to comprehensively and prospectively study the biological characteristics of this selected group of patients, which will allow to improve their future clinical-biological identification and to deepen the knowledge of the response and resistance mechanisms. to new drugs. For this reason it has been contemplated to associate an extensive and complete molecular study, which includes the total sequencing of exomes from these patients.

MCL similarly to what has been observed in other lymphoproliferative disorders, could show subclonal heterogeneity even at diagnosis and this fact might condition the ulterior clinical behaviour of the tumor (10). In addition, there has been recently described the involvement of the alternative NF- $\kappa$ B pathway in the resistance of BCR inhibitors by the identification of several mutations in NF- $\kappa$ B regulatory genes that confer resistance to these biological agents (11).

This observation enhances the need of collecting fresh samples in the setting of well-designed trials to elucidate the role of new therapies in these patients. As peripheral blood is involved in a

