### 3.3 TREATMENT PLAN

Subjects will receive ibrutinib in combination with rituximab according to the following schedule:

- Ibrutinib 560 mg daily po for 28 days (cycle one). Continuous cycles until disease progression or unacceptable toxicity. In case of sustained negative MRD (at least for 6 months) after 2 years of continuous therapy, ibrutinib will be discontinued.
- Rituximab 375 mg/m^2 iv day 1, 8, 15 and 22 (cycle 1, 4 doses). Rituximab 375 mg/m^2 iv, day one of every other cycle for 4 doses (cycle 3, 5, 7 and 9).

This clinical trial includes:

- Central review of response by imaging.
- Histological central laboratory review of diagnosis.
- Biological Associated Project.

Within a maximum of 28 days pre-treatment study test will be performed (except BMO and PET-CT, that are admissible if are obtained within six months and three months respectively in patients with clinical stability) and then the medication is started. Tests to be performed and related details are described in section 4.2 of this protocol.

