Reactivation of hepatitis B, which included cases of fulminant hepatitis in patients who were treated with rituximab with cytotoxic chemotherapy have been observed. When rituximab is used in combination with cytotoxic chemotherapy, patients with a history of hepatitis B should be closely monitored for signs of active infection by the hepatitis B virus, and start antiviral treatment if clinically indicated.

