#### b. Hepatitis B reactivation prophylaxis

Lamivudine or other antiviral treatments have to be considered to patients at risk of reactivation of hepatitis B (i.e. HBcAc+).

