**Version 3.2: September 16th, 2020**

### 5.2.1 Screening Phase:

Within a maximum of 28 days\* prior to treatment initiation, it should be determined and collected the following clinical and laboratory data:

- Informed consent.
- Date of birth, date of diagnosis, medical history and concomitant medication.
- Physical examination, ECOG and vital signs.
- Quality of Life questionnaires.
- Local laboratory pathology diagnosis. The tissue FFPE block or slides will be sent to the central pathology laboratory to confirm the diagnosis and the Ki-67 proliferation rate whenever possible. The timeline of 28 days for the central review is not strict.
- CBC (hemoglobin, leucocytes with differential count and platelets).
- Biochemistry: creatinine, urea, uric acid, Na, K, Ca, glucose, total protein, protein electrophoresis, albumin, IgG assessment, IgA and IgM, bilirubin, alkaline phosphatase, GGT, AST, ALT, LDH and  $\beta_2$  seric microglobulin, serum immunofixation.
- Coagulation; TP, TTP, fibrinogen.
- Pregnancy test (performed on blood or urine) in women of childbearing potential.
- Hepatitis B and C (including anti-core VBH) and HIV serology.
- Disease assessment by PET/CT.
- Electrocardiogram.
- Left ventricular ejection fraction (optional, only mandatory in patients with a history of heart disease).
- Bone marrow biopsy.
- Bone marrow aspirate (with local study by flow cytometry and sending to MRD determination) ~~is optional, but recommended in cases exclusively involving bone marrow and peripheral blood.~~
- Concomitant medication.
- Tumor samples for molecular sub-study and MRD study. It will be obtained 30-50 ml of peripheral blood for shipment to central laboratory. Other territories will be considered based on clinical presentation, availability of samples (exceeding from diagnosis) and method of sample preservation.

\* Baseline laboratory should be performed within 7 prior days at the most. The PET-CT and BMB obtained within 3 and 6 months prior to enrolment in the study respectively, will be accepted as a baseline examination in patients who meet study eligibility criteria. A broader interval may be considered for these baseline tests according to specific cases

\*\* If the central review does not confirm the pathological diagnosis, the patient must be withdrawn from the study.

Version 3.2: September 16th, 2020

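### Exclusion 12 gives HBcAb-positive patients with protective HBsAb two entry rules and no precedence; the monitoring sentence in 3.5.2 does not reach this regimen, and 3.7b is weaker than the stricter entry rule

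*Protocol*

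**What the plan says.** Exclusion 12 stands in the same form in section 4.2 and in the synopsis. It excludes active or chronic hepatitis B and then lists exceptions. The first is "Patients with occult or prior HBV infection (defined as negative HBsAg and positive total HBcAb) may be included if HBV DNA is undetectable", subject to willingness to have monthly DNA testing or antiviral prophylaxis. The second follows at once: "Patients who have protective titers of hepatitis B surface antibody (HBsAb) after vaccination or prior but cured hepatitis B are eligible".

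Two later sections deal with hepatitis B during treatment:

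- Section 3.5.2: "When rituximab is used in combination with cytotoxic chemotherapy, patients with a history of hepatitis B should be closely monitored" for signs of active infection, with antiviral treatment if clinically indicated.
- Section 3.7, item b: "Lamivudine or other antiviral treatments have to be considered to patients at risk of reactivation of hepatitis B", with core-antibody positivity given as the description of the at-risk patient.

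On the regimen, section 3.3 says "Subjects will receive ibrutinib in combination with rituximab according to the following schedule", and section 2.1 speaks of "treating in front-line selected MCL patients with a chemo-free approach". Screening in section 5.2.1 includes "Hepatitis B and C (including anti-core VBH) and HIV serology", so core-antibody status is known for every patient.

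**The concern.** The first exception shows what the authors intend for a patient with past hepatitis B: a DNA check before entry, then either monthly DNA testing or prophylaxis. The second exception can be read as releasing part of that same group from all of it.

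A site that reads it so, and then considers antivirals under 3.7b and decides against them, could treat an HBcAb-positive patient with no DNA test, no prophylaxis and no close monitoring, and still be following these protocol sections. Another site would apply every safeguard to an identical patient. What is at stake is patient safety and consistent practice between sites. Section 3.5.2 itself reports hepatitis B reactivation, including fulminant cases, with rituximab plus cytotoxic chemotherapy.

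**Working it through.** There is no plan figure to reproduce. The check is a comparison of text, followed by dates to see whom a change could still reach.

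**1. Do the two sentences of exclusion 12 overlap?**

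| Serology (HBsAg negative throughout) | First exception | Second exception |
|---|---|---|
| HBcAb negative, protective HBsAb after vaccination | does not apply | eligible, no condition |
| HBcAb positive, HBsAb not protective | eligible with conditions | does not apply if protective HBsAb is required |
| HBcAb positive, protective HBsAb after cured infection | eligible with conditions | eligible, no condition |

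The third row falls under both. HBsAb plays no part in the definition used by the first exception, so a protective titre does not take the patient out of it. The second exception can also be parsed so that cured hepatitis B stands alone, without the titre requirement. The overlap then remains and becomes wider. The hepatitis C sentence that follows makes eligibility expressly conditional on a negative RNA result, so a reader may fairly take the absence of a condition in the hepatitis B sentence as meant.

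**2. Do later sections settle it?**

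| Section | Reaches ibrutinib plus rituximab? | What it requires |
|---|---|---|
| Exclusion 12, first exception | yes | undetectable DNA, and monthly DNA testing or prophylaxis accepted |
| 3.5.2 | no; triggered by cytotoxic chemotherapy | close monitoring |
| 3.7b | yes; no chemotherapy condition | antivirals to be considered |

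Section 3.5.2 never applies as written. Section 3.7b applies in full but sets a lower duty and does not mention DNA testing.

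**3. Whom could a change still reach?** The synopsis calendar gives inclusion from May 2016 to December 2019. Version 3.2 is dated 16 September 2020. I take 1 May 2016 and 31 December 2019 as the outer inclusion dates.

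- Earliest patient: 1,599 days, or 1,599 / 30.44 = 52.5 months (4.4 years).
- Latest patient: 260 days, or 260 / 30.44 = 8.5 months.

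Both lie inside the 7-year limit of section 5.2.5, so every patient was still in the study unless progression, death, withdrawal or loss had intervened.

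The last rituximab dose is on day 1 of cycle 9, that is study day (9 − 1) × 28 + 1 = 225. Counting from a start on 31 December 2019, this is 11 August 2020, 36 days before version 3.2. Without delays, rituximab was over for everyone. Ibrutinib could continue, though section 3.6 stops it in patients with sustained negative MRD after 2 years.

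**4. How many patients?** The protocol gives no prevalence. As an assumption only, with prevalence p among 50 patients, the expected number is 50p and the chance of no such patient is (1 − p)^50.

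| Assumed p | Expected number | Chance of none |
|---|---|---|
| 1% | 0.5 | 0.605 |
| 2% | 1 | 0.364 |
| 5% | 2.5 | 0.077 |
| 10% | 5 | 0.005 |

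The row to use differs between the overlap group and all HBcAb-positive patients, since the first is a subset of the second. The table shows that zero is quite possible at low prevalence. It does not estimate the number.

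**The case against.** The best defence is that the two sentences can be obeyed together. The first defines its group by serology alone, so a site that applies its conditions to every HBcAb-positive patient breaches nothing. That is right. A reader might infer that exclusion 12 contradicts itself; it does not. It is ambiguous, and the weaker reading is open because no precedence is stated.

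A reader might also infer that the protocol has no hepatitis B provision that works for this regimen. Section 3.7b refutes that: it carries no chemotherapy condition and names core-antibody-positive patients. It is weaker than exclusion 12, not absent.

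Thirdly, sections 3.4.3 and 3.4.4 send sites to the Investigator's Brochure and the product information for warnings and precautions, and the revision sheet for version 2.0 records that ibrutinib safety information was cross-referenced on purpose. Those sources may require more. They are not shown, so it cannot be said that patients went unprotected. Nor do they correct a sentence in 3.5.2 whose condition leaves out the trial's own treatment.

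Finally, one might press the lack of a stop point for monthly DNA testing, or the move to three-monthly visits after year 1. These are missing detail, not conflicts: blood can be drawn monthly between study visits.

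**Conclusion.** The point holds as a minor safety-wording issue. One serological profile falls under a conditional and an unconditional eligibility sentence with no rule of precedence. The monitoring sentence in 3.5.2 depends on chemotherapy that the trial does not use, and 3.7b asks for less than exclusion 12.

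The size is limited. The number of patients concerned is unknown and may be zero. On the planned dates recruitment had ended before version 3.2, so rewording the criterion changes no planned entry. The practical effect is on enrolled HBcAb-positive patients still on treatment or in follow-up.

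It would be tempting to read the reported fulminant hepatitis as the risk in this trial. The protocol reports it with rituximab plus cytotoxic chemotherapy, and its own text states no reactivation risk for rituximab with ibrutinib. The sample size, the primary endpoint and the error rates are unaffected.

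The conclusion rests on the protocol text alone, on the calendar dates being kept, and on the cited product information being unavailable here.

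**What to change.** 1. In exclusion 12 (section 4.2 and synopsis), limit the sentence without conditions to vaccinated, HBcAb-negative patients, so that every HBcAb-positive patient follows the conditional rule.
2. In section 3.5.2, delete the cytotoxic-chemotherapy qualifier from the monitoring sentence.
3. In section 3.7b, match exclusion 12: antiviral prophylaxis or monthly HBV DNA testing for HBcAb-positive patients. Keep the monthly interval; a general reference to DNA monitoring would loosen the existing rule.
4. Apply items 2 and 3 to enrolled HBcAb-positive patients still on treatment or in follow-up.

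The cost is wording in four places and no new serology, because core antibody is already tested at screening. HBV DNA tests fall on HBcAb-positive patients who are not on prophylaxis. For those admitted under the conditional sentence the testing is already foreseen; for any patient admitted under the sentence without conditions it would be new.

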### 4.3 PROHIBITIONS AND RESTRICTIONS

The following guidance should be applied during the perioperative period for subjects who require surgical intervention or an invasive procedure while receiving ibrutinib:

For any surgery or invasive procedure requiring sutures or staples for closure, ibrutinib should be held at least 7 days prior to the intervention and should be held at least 7 days after the procedure, and restarted at the discretion of the investigator when the surgical site is reasonably healed without serosanguineous drainage or the need for drainage tubes.

For minor procedures (such as a central line placement, needle biopsy, thoracentesis, or paracentesis) ibrutinib should be held for at least 3 days prior to the procedure and should not be restarted for at least 3 days after the procedure. For bone marrow biopsies that are performed while the subject is on ibrutinib, it is not necessary to hold ibrutinib for these procedures.

For emergency procedures, ibrutinib should be held after the procedure until the surgical site is reasonably healed, for at least 7 days after the urgent surgical procedure.

### 4.4 PREMATURE DISCONTINUATION/END OF STUDY CRITERIA

It will encourage patients to **comply with the treatment, visits and procedures scheme until the end of the study is reached as described in section 5.2.5** ~~complete the trial~~, however, patients can voluntarily leave the trial at any time.

~~The investigator may also, at its discretion, withdraw patients from this trial, or the Sponsor may discontinue the trial.~~

The reasons for premature study discontinuation **by the patient** should be documented in the case report form (CRF) as:

- ~~● The trial is closed/ended.~~
- Patient lost of follow up.
- ~~● Investigator decision.~~
- Patient informed consent withdrawal .
- ~~● Major protocol deviation, when applicable.~~
- Death.

Both the date of withdrawal from the study and the cause of withdrawal will be recorded in the CRF.

Post-treatment and follow-up up to death will be determined ensuring the patient's medical care according to clinical practice. In case of death, it should as far as possible, to obtain the certificate with the cause of death.

Note: Patients who leave the trial for any reason, will not be enrolled again.

Version 3.2: September 16th, 2020

## 5. STUDY DEVELOPMENT AND RESPONSE ASSESSMENT

### 5.1 STUDY ENDPOINTS

#### Primary Endpoint:

1. Rate of complete remission (CR) achieved at 12 months with Ibrutinib in combination with Rituximab. All the patients will be evaluated with PET-CT and bone marrow biopsy at that point and the international response criteria will be applied (13).

